3.2.1 Main Indicators and Definitions

2-year progression-free survival rate (2-year PFS rate): the rate of no tumor progression or death from any cause within 2 years from postoperative treatment (whichever comes first).

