3.2.2 Secondary indicators and Definitions

Duration of response (DOR): the time between the start of CR or PR and the first assessment of PD or death from any cause.

Objective response rate (ORR): the proportion of patients with a 20% tumor reduction for a certain period of time, including complete response (CR) and partial response (PR). The ORR was defined as the proportion of patients with a 20% tumor size reduction in the shortest time period.

3.2.3. safety indicators

The subject's vital signs, blood routine, liver function, blood biochemistry, urine routine, stool routine, coagulation function, left ventricular ejection fraction (LVEF), creatine phosphokinase, vitamin E, and bleeding risk.

4. study population

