5.1 Overall design (including assumptions, type, etc.)

This study hypothesized that selmetinib hydroxyl sulphate capsules are effective in neurofibromatosis type I, including improving efficacy after tumor resection, delaying progression, reducing recurrence, and improving function. The prospective, single-arm, phase-study study protocol was designed to estimate progression-free survival (PFS) in more than 50% of NF 1 patients at 24 months, objective response rate (ORR) of 40%, and duration of tumor response (DOR) of 12 months.

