5.4 Definition of end of study (e. g. last subject completes last follow-up)

5.5 Statistical analysis

5.5.1 Sample size and basis for calculation

The estimated sample size was based on the objective response rate. The hypothesis of this study is that selmetinib sulphate can reduce the recurrence rate of patients after NF 1. The study parameters were set: $\alpha = 0.025$ (unilateral), Power=80%, and progression-free survival (PFS) in 20% of patients with NF 1 for 24 months. More than 50% of progression-free survival (PFS) in NF 1 patients. 17 cases were calculated using PASS 15.0 software, considering 10% shedding rate, 19 subjects should be included.

.5.52 Data analysis set (e. g. full analysis set, compliance protocol set, safety analysis set)

Statistical analysis will be performed using the SAS statistical software (V. 9.4, SAS Institute) Statistical analysis software for calculation, if no special instructions, the main indicators use one-sided test, control the first class error α is 0.025, the remaining indicators use two-sided test, one class error is $\alpha = 0.05$. To calculate confidence intervals, calculate two-sided 95% confidence intervals if not otherwise specified.

(1) Full analysis set (full analysis set, FAS): consisting of all subjects who received at least one drug / treatment and obtained efficacy assessment. This dataset was derived from all subjects after removing subjects in the least and reasonable way.

(2) Safety analysis set (safety analysis set, SS): a population treated at least once / once and having at least one safety evaluation data. In the safety analysis, all patients will be analyzed by the actual drug group.

(3) Compliance with the protocol set (per-protocol set, PPS): all concomitant medications that met the trial protocol and did not use the

impact effectiveness evaluation, good medication compliance (between 80% and 120%), excluded subjects who had major protocol violations and were judged to have a significant impact on the results. All protocol deviations causing the exclusion of subjects from the compliant protocol set will be described in detail in the Statistical Analysis Plan (SAP) and completed prior to data lock.

5.3 5 Statistical analysis plan

Data description of statistical analysis, analysis method of primary / secondary indicators / safety indicators, statistical school positive method, control of bias, stratification / subgroup / sensitivity analysis, etc

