Demographic, and other baseline characteristics

Based on the analysis of FAS set, the demographic data, medical history, vital signs and other baseline data were statistically described, where the measurement data (age, BMI, XX, etc.) gave mean, SD, minimum, maximum, median, and gave frequency and corresponding percentage for count data (gender, XXX, etc.).

Analysis of efficacy indicators

(1) Main efficacy indicators

Point estimates for the main evaluation index (PFS) and estimated two-sided 95% confidence intervals using the Clopper–Pearson exact probability method. If the lower limit of the 97.5% confidence interval is greater than the proportion of 24 months, the treatment group was considered better effective than the historical control.

We obtained the analysis model:

$$Y = b_0 + b_1 \cdot X_1 + b_2 \cdot X_2 + b_3 \cdot X_3 + \epsilon$$

In this equation, the X_i Represents the extent of tumor resection,

X_2 Represents the solid tumor size, X_3 Indicates the medication dose. b_0 Is the intercept, b_1 , b_2 , b_3 Is the regression coefficient of each factor, and the ϵ is the error term.

(2) Secondary efficacy indicators: analysis using FAS and PPS analysis sets. For survival measures, the digit survival time and its two-sided 95% confidence intervals were calculated. For the rate of each index, point estimates were performed and two-sided 95% confidence intervals were estimated using the Clopper-Pearson exact probability method. For the continuity index, the mean and two-sided 95% confidence intervals were calculated based on the normal distribution method, otherwise, the median and two-sided 95% confidence intervals were calculated based on the percentile method.

Safety index analysis

The SS set describes the incidence of adverse events / serious adverse events and adverse reactions, and lists the details of each adverse event in each subject, including the type and severity of adverse events. Safety and evaluation of laboratory indicators, vital signs, electrocardiogram and other safety related indicators, compare and evaluate the changes before and after treatment, and give statistical description of clinical evaluation (normal, abnormal without clinical significance, abnormal with clinical significance, not checked) before and after treatment.

Principles of handling of missing / deleted / lost to follow-up data

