Main index analysis adopts LOCF (last observation carried forward) method, that is, the main index data is not observed at the last time; the secondary indicators and safety indicators are not filled.

6. Research intervention*

6.1 Study intervention content (description of intervention content, implementation steps, dose and route of intervention drug, frequency of intervention, product of test group and control group, etc.)

All patients received oral selmetinib hydrosulphate capsules (20–50mg bid) daily for 30 days for 6 cycles, based on individualized patient body surface area (BSA).

6.2 Preparation / handling / storage / responsibilities (drug versus control article allocation plan when intervention should be specified)

The use of drugs must be recorded in the patient's medical record and in the corresponding location of the CRF. After the enrollment of the subjects and at the 1 and 2 months of follow-up, the executive nurse shall receive the corresponding number of drugs at the drug administrator, and the remaining drugs and boxes shall be returned to the drug administrator. If the drug is found or damaged during the preparation process, this box of drugs should not be used, the damaged drugs shall be treated as empty bottles, and other undamaged drugs shall be returned to the drug administrator together with the packaging box. The study center shall be responsible for the management of test drugs, including receiving, distribution, counting and recovery. The investigator shall ensure that the test drug is stored in a safe, independent and locked place at the study site and the storage conditions shall meet the storage requirements of the test drug. No one can be contacted without the consent of the investigator. Empty boxes shall be stored and managed as the test drug.

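### The full analysis set leaves out treated subjects who were never assessed, which inflates the ORR and possibly the 2-year PFS rate

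*Protocol*

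**What the plan says.** Section 5.5.2, item (1), sets two conditions for the FAS: treatment, and an efficacy result. It is described as "consisting of all subjects who received at least one drug / treatment and obtained efficacy assessment". The next sentence adds an aim: "This dataset was derived from all subjects after removing subjects in the least and reasonable way".

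The analysis paragraph for the secondary endpoints reads "Secondary efficacy indicators: analysis using FAS and PPS analysis sets". ORR is one of these endpoints, and section 3.2.2 defines it as "the proportion of patients with a 20% tumor reduction for a certain period of time". Section 5.1 anticipates an "objective response rate (ORR) of 40" per cent.

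On missing data, the protocol says "Main index analysis adopts LOCF (last observation carried forward) method", while "the secondary indicators and safety indicators are not filled".

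The paragraph on the main efficacy indicator gives an exact Clopper-Pearson interval but names no analysis set. Section 3.2.1 makes death from any cause an event for the 2-year PFS rate. Section 7.2 permits follow-up after withdrawal but does not require it.

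**The concern.** Whether a subject obtains an efficacy assessment is settled after treatment starts, and it may depend on how the subject fares. Someone who dies, deteriorates or gives up early is the person most likely to have no follow-up scan. In the schedule of section 5.2.1 (column headings lost) imaging is ticked in the first column and not again until the fifth of eleven, so there is an interval in which this can happen.

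For ORR the consequence follows directly from the text. The unassessed subject is outside the FAS, and no rule for secondary endpoints brings that subject back as a non-responder. Such a subject has no documented response, so the exclusion removes only from the denominator and the rate can only rise. The sentence about minimal removal states an intention and does not override the condition before it.

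For the 2-year PFS rate the point is conditional. If the FAS is meant, which is likely, an early death without imaging could drop out although death is an event, unless a recorded death is read as an efficacy assessment. Early dropouts would leave too, but their 24-month status is unknown rather than failed. Stopping the drug does not by itself exclude anyone.

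The trial has a single arm of 19 subjects, so no comparator shares the bias and each excluded subject carries visible weight.

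**Working it through.** **Inputs.** From section 5.5.1: reference 24-month PFS 20%, target 50%, one-sided alpha 0.025, power 80%, 17 evaluable, 10% loss, 19 enrolled. From section 5.1: ORR 40%. Not given: the share e of treated subjects lost before any efficacy assessment, and the share s of those who are truly progression-free at 2 years. I show e = 5% and 10% as assumptions; 10% is the plan's total loss.

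**The plan's own figure.** The normal approximation ((1.96·√(0.2·0.8) + 0.842·√(0.5·0.5)) / 0.3)² = 16.13, rounded up to 17. Then 17/0.9 = 18.9, rounded up to 19. Both figures reproduce.

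**ORR, 19 treated, unassessed subjects excluded** (two-sided 95% Clopper-Pearson interval for 7 responders):

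| Excluded | 7 responders | 8 responders |
|---|---|---|
| 0 | 7/19 = 36.8% (16.3–61.6) | 8/19 = 42.1% |
| 1 | 7/18 = 38.9% (17.3–64.3) | 8/18 = 44.4% |
| 2 | 7/17 = 41.2% (18.4–67.1) | 8/17 = 47.1% |

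Each exclusion adds about 2 to 3 points. In expectation the reported ORR is p/(1 − e): 0.40/0.95 = 42.1% and 0.40/0.90 = 44.4%.

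**2-year PFS, only if the FAS is used.** Reported rate = (p − e·s)/(1 − e), with p = 0.50:

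| e | s = 0 | s = 0.25 | s = 0.50 |
|---|---|---|---|
| 5% | 52.6% | 51.3% | 50.0% |
| 10% | 55.6% | 52.8% | 50.0% |

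The s = 0 column is the worst case. At s = 0.50 there is no bias.

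**Primary decision.** The pass mark is the smallest x with P(X ≥ x | n, 0.20) ≤ 0.025. It is 8 at n = 16 (0.0070), 17 (0.0109), 18 (0.0163) and 19 (0.0233). Seven successes still fail after three exclusions (7/16, lower limit 19.75%). The verdict flips only at four exclusions (7/15, lower limit 21.3%).

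**Type I error when every unassessed subject is a failure.** Sum over k of Bin(k; 19, e) × P(X ≥ pass mark at 19 − k | 19 − k, 0.2/(1 − e)). This gives 0.0233 at e = 0, 0.0235 at 5% and 0.0257 at 10%.

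**Interaction with LOCF if the FAS is widened.** Take 6 true successes in 19 and two never-assessed subjects, and compare the lower 95% limit with 20%:

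- excluded, as the FAS now stands: 6/17, lower limit 14.2%, fails;
- kept as failures: 6/19, lower limit 12.6%, fails;
- kept and carried forward as progression-free: 8/19, lower limit 20.3%, passes.

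**The case against.** The strongest reply is that little turns on this. No test or success rule is attached to ORR. The 40% is an expectation, and a shift from 36.8% to 41.2% is small beside an interval about 45 points wide. The two-subject example puts the whole planned loss before the first assessment, although that loss is spread over a study with a 24-month endpoint. The PFS part depends on an analysis set that may be named in a statistical analysis plan not shown here, and the primary verdict does not change. Counting an unobserved response as non-response is also a convention. Finally, the LOCF hazard arises only once the set is widened.

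Much of this stands as a limit on size. Two exclusions is an upper illustration, one exclusion moves ORR by about 2 points, and the PFS bias could be zero. The reply does not remove the point itself. The FAS condition and the rule against filling secondary data are stated in the protocol, and a statistical analysis plan that follows them would carry the exclusion forward. Counting unassessed subjects as non-responders is the standard conservative convention for ORR. The LOCF sentence is a safeguard that the corrected set needs; it adds no weight to the defect.

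**Conclusion.** The concern holds for ORR as the protocol is written, and for the 2-year PFS rate on condition that the FAS is its analysis set. Each treated but unassessed subject raises the reported ORR by about 2 to 3 points, and two of them can carry it from below to above the anticipated 40%. For PFS, a true 50% would be reported as 50.0% to 52.6% at 5% unassessed and as 50.0% to 55.6% at 10%.

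The harm is an inflated estimate in a trial without a comparator. It is not a false positive on the primary test: dropping one to three failures leaves the verdict unchanged, and the worst-case type I error is 0.0257.

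This rests on reading efficacy assessment as a post-baseline assessment, on 20% as the reference proportion, and on assumed shares of unassessed subjects. The change should be made, though the primary analysis does not fail without it.

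**What to change.** - In section 5.5.2, define the FAS as all subjects who received at least one dose, and name it as the set for both the 2-year PFS rate and ORR.
- For ORR, count subjects without a post-baseline tumour assessment as non-responders.
- For PFS, count any death within 2 years as an event, whether or not imaging was done.
- In the planned Clopper-Pearson proportion, keep treated subjects without a post-baseline assessment in the denominator as not progression-free.
- In the missing-data paragraph, state that LOCF does not carry such subjects forward as progression-free.
- A Kaplan-Meier estimate can be added as a sensitivity analysis.

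The cost is four or five sentences across section 5.5.2, the main-efficacy paragraph and the missing-data paragraph, with no new data and no change to the sample size. The drawback is slightly lower, conservative estimates, because some subjects counted as PFS failures may in truth be progression-free.

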4.2 Exclusion criteria

(1) The patient had abnormal blood indexes, abnormal liver and kidney heart function, and cannot tolerate the clinical study process after multidisciplinary consultation and evaluation

(2) The patient has become malignant peripheral nerve schwannoma (MPNST) or has serious complications such as other malignant tumors and heart disease, or has been treated with anti-tumor therapy such as chemotherapy and radiotherapy

(3) The whole clinical study cannot be completed due to personal, social and economic reasons

(4) There are previously serious systemic system diseases and the disease cannot be cured or drug control

(5) Patients who are present in pregnancy

4.3 Lifestyle considerations (lifestyle related restrictions: smoking, drinking, exercise, diet, etc., and what measures will be taken if the subject needs drugs, treatments or surgery prohibited in the protocol)

After entering the clinical study, the subject needs a light diet, food, tobacco, alcohol, and no strenuous exercise. If the subject needs

the drug, treatment or surgery unrelated to the study, the investigator needs to evaluate whether the cause of the need for the drug, treatment and surgical treatment is the adverse event of the study, additional treatment due to accident or other reasons, consider the impact of the treatment on the course of the study, then advise the subject to receive conventional treatment after withdrawal and seal the subject data.

4.4 Screening failures (definition of screening failures and how to process screening failed subjects)

Screening failure refers to the recruitment of subjects who failed to meet the inclusion criteria or the exclusion criteria after multidisciplinary evaluation. The study will inform the results of the multidisciplinary consultation and give the current best treatment advice.

4.5 Recruitment and retention strategy (how to recruit subjects (location, method, expected number.....); How to retain subjects (multiple contact information, incentive); such as involving vulnerable groups: reason + safeguard measures; if having compensation or incentive measures: object, quantity, form, time, etc.)

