6.4 Concomitant therapy (permitted adjuvant medication, complementary / replacement therapy)

If the subject has hypertension, diabetes, coronary heart disease and other diseases that need long-term drug control, the investigator and the relevant specialist should evaluate the impact of the disease and the relevant study protocol and determine the dose and duration of adjuvant medication.

6.4.1 Rescue (drug, treatment methods, relevant records.....)

The life hazards during the implementation of the clinical study protocol should be implemented in accordance with the clinical rescue plan, such as cardiopulmonary resuscitation, emergency airway management, emergency surgical treatment, relevant records during hospitalization should be recorded in the medical record system, after discharge should be recorded in the adverse event record form, and the investigator should analyze whether the rescue causes are related to the study and discuss and discuss synchronously in the rescue records.

7. Discontinuation of the study intervention / subject discontinuation and withdrawal*

7.1 Study Intervention discontinuation (reasons / criteria: such as how many adverse events occurred, length of study discontinuation, how data were collected during discontinuation and how to reactivate the study intervention, whether follow-up was continued during discontinuation)

If the Grade 5 adverse event of CTCAE 5.0 standard reaches 10% of the number of subjects, the study should be discontinued and the drug safety of the study protocol should be discussed to determine whether to adjust the dose of drugs in the study protocol, continue the follow-up during the study suspension, and maintain the follow-up record of the original

subject.

7.2 Subjects discontinuation / withdrawal from the study (possible reason for subject discontinuation; involving implantable device, discuss how to remove / replace, obtain alternative materials, later contact with the subject, etc.)

When the subject stops or withdraws from the study due to dissatisfaction with the treatment effect of the study plan or his own economic reasons, he should actively communicate with the subject, encourage the subject to actively treat and help them apply for public welfare funds to complete the treatment. If the subject clearly withdraws, the investigator can continue to complete the follow-up without the study intervention.

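### LOCF on the primary 2-year PFS rate scores patients lost while progression-free as successes, so it can bias the rate only upward and inflates the type I error

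*Protocol*

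**What the plan says.** Section 3.2.1 defines the main index as "2-year progression-free survival rate (2-year PFS rate): the rate of no tumor progression or death from any cause within 2 years from postoperative treatment". Section 5.5 (analysis of efficacy indicators) analyses it as a simple proportion with a Clopper-Pearson interval. The success rule begins: "If the lower limit of the 97.5% confidence interval is greater than the proportion of 24 months", in which case the treatment is judged better than the historical control. The benchmark is not repeated there. Section 5.5.1 gives "progression-free survival (PFS) in 20% of patients with NF 1 for 24 months" as a design parameter, so 20% is the natural reading.

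The paragraph on missing data at the end of Section 5.5 reads: "Main index analysis adopts LOCF (last observation carried forward) method, that is, the main index data is not observed at the last time". Secondary and safety data are left unfilled. The words after the method's name are garbled, but the method is named and assigned to the main index. For the primary endpoint the protocol gives no censoring rule, no Kaplan-Meier estimate and no rule that counts lost patients as failures.

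Three other places bear on who is lost:

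- Section 5.5.1 allows for 10% shedding.
- Section 7.2 lists "dissatisfaction with the treatment effect of the study plan or his own economic reasons" as grounds for stopping or withdrawing, and adds: "If the subject clearly withdraws, the investigator can continue to complete the follow-up without the study intervention".
- Section 4.3, on treatment needed for reasons unrelated to the study, says to "then advise the subject to receive conventional treatment after withdrawal and seal the subject data".

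**The concern.** LOCF is a rule for measurements that can move either way. Here the outcome is an absorbing event. A patient who has progressed or died is a failure whatever happens later, so carrying that forward changes nothing. A patient last seen progression-free is recorded as having reached 24 months progression-free, whether or not that happened. Errors run in one direction only, towards the treatment.

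The trial has one arm, so no control group shares the bias, and the only formal efficacy decision compares this rate with a fixed number. With 19 patients, each one is worth 1/19 = 5.3 percentage points. Dissatisfaction with the treatment effect is an expected reason for leaving, so loss may precede progression. Follow-up after withdrawal is permitted but not required.

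**Working it through.** **Inputs.** From Section 5.5.1: null rate 20%, alternative 50%, one-sided alpha 0.025, power 80%, 17 patients before and 19 after 10% shedding. The timing and pattern of loss are not in the protocol and are assumed below.

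**1. The plan's own figure.** Normal approximation with null variance:

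n = [1.960·√(0.2·0.8) + 0.842·√(0.5·0.5)]² / (0.5 − 0.2)² = (0.784 + 0.421)² / 0.09 = 16.13, rounded up to 17; 17/0.9 = 18.9, rounded up to 19.

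Both stated numbers are reproduced, which supports 20% as the benchmark.

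**2. The decision rule in counts.** Success needs a Clopper-Pearson lower limit above 0.20.

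- Two-sided 95% interval (the same as a one-sided 97.5% limit), n = 19: 7/19 gives 0.163 and 8/19 gives 0.2025, so the cut-off is 8. Size P(X≥8 | 19, 0.2) = 0.0233; power P(X≥8 | 19, 0.5) = 0.820.
- 97.5% interval read as two-sided, n = 19: 8/19 gives 0.180 and 9/19 gives 0.220, so the cut-off is 9. Size 0.0067.
- Two-sided 95% interval, n = 17: 8/17 gives 0.230, so the cut-off is 8. Size 0.0109.

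**3. LOCF under the null.**

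*A. Independent loss.* Take exponential PFS with λ = −ln(0.2)/24 = 0.06706 per month, and exponential loss with μ = −ln(1−d)/24, where d is the probability of loss by month 24 if the patient never progressed. The LOCF success rate is

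1 − λ/(λ+μ)·(1 − e^(−24(λ+μ))).

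For d = 10%, μ = 0.00439 and the rate is 1 − 0.9386·(1 − 0.18) = 0.230. Then P(X≥8 | 19, 0.230) = 0.051. Only 0.230 − 0.180 = 5.0% of patients are actually lost while progression-free here, because many progress first.

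*A′.* The same model, with μ set so that 10% of all patients are actually lost while progression-free: rate 0.261.

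*B. Two early losses, both carried forward.* Only six more successes are needed from 17: P(X≥6 | 17, 0.2) = 0.106.

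*C. Informative extreme.* 10% of all patients are lost just before they would progress: rate 0.20 + 0.10 = 0.30, and P(X≥8 | 19, 0.3) = 0.182.

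| Loss pattern | Expected rate, n = 19 | Type I error, ≥8/19 | ≥9/19 | ≥8/17 |
|---|---|---|---|---|
| None | 20.0% | 2.3% | 0.7% | 1.1% |
| A, d = 5% | 21.5% | 3.5% | 1.1% | 1.7% |
| A, d = 10% | 23.0% | 5.1% | 1.7% | 2.5% |
| A, d = 20% | 26.2% | 9.8% | 3.9% | 5.2% |
| A′, 10% lost progression-free | 26.1% | 9.6% | 3.7% | 5.1% |
| B, two early losses | 28.4% | 10.6% | 3.8% | 6.1% |
| C, 10% lost just before progression | 30.0% | 18.2% | 8.4% | 10.5% |

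**4. Direction.** In 100,000 simulated trials under A′, the LOCF rate never fell below the complete-data rate in the same patients. The mean Kaplan-Meier estimate was 20.0%.

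**5. The alternatives, n = 19.**

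- Lost patients counted as failures, 10% independent loss: null rate 0.2·0.9 = 0.18, size P(X≥8 | 19, 0.18) = 0.013; power at 0.5·0.9 = 0.45 is P(X≥8 | 19, 0.45) = 0.683. In pattern C the size stays at 0.023.
- Kaplan-Meier at 24 months with log-log limits (simulated): with 10% independent loss, size just under 2% and power about 75%. In pattern C the mean estimate is about 24.5% and the size about 4.8%.

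**The case against.** The strongest objection is that the size of the effect is not known. A lost patient who would in fact have reached 24 months progression-free is scored correctly, and if all losses fall close to month 24 the error stays near 2.3%. That is right. The bias is zero only if every lost patient would have stayed progression-free.

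Under moderate independent loss (A, d = 10%) the error clearly exceeds 2.5% only with the 8/19 cut-off, and the larger figures rest on assumed patterns. This also stands, and is why a range is given. The n = 17 column can be criticised for applying loss to a number already net of shedding, so it is best read as a secondary range. Pattern B needs the two patients to have had an efficacy assessment, because the full analysis set otherwise excludes them.

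The protocol does try to limit loss: Sections 6.3 and 7.3 require telephone contact and multiple contact details. That may reduce the number of losses but does not change how they are scored. The sealing of data in Section 4.3 covers a particular group and may only mean archiving, so it is weak evidence on its own.

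Finally, Kaplan-Meier could be the primary analysis instead. It costs less power, but it is valid only if loss is unrelated to coming progression, and pattern C shows that it does not protect the error rate when that fails.

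**Conclusion.** The concern holds and should be fixed before any primary analysis. The protocol fixes LOCF for an endpoint it does not suit, and nothing elsewhere replaces it. Against complete data in the same patients, the rule can only raise the 2-year PFS rate. The type I error rises under every reading of the decision rule as soon as any lost patient might have progressed.

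At 8/19 and a 20% benchmark, it goes from 2.3% to 5.1% under 10% independent exponential loss and to 18.2% in the informative extreme. Whether it passes the nominal 2.5% under the stricter cut-offs depends on the loss pattern. The 20% benchmark is inferred from Section 5.5.1, and the loss patterns are assumptions.

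**What to change.** Delete LOCF for the primary endpoint, in the protocol and in the statistical analysis plan if it repeats the rule. Suggested text:

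*In the full analysis set, a patient counts as progression-free at 24 months only if a tumour assessment at or after 24 months shows no progression or earlier death. A patient without such an assessment counts as not progression-free. The lower limit of the two-sided 95% Clopper-Pearson interval is compared with 20%.*

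This keeps the exact method already planned and cannot score a lost patient too favourably. The protection covers only patients in the full analysis set, so also state how a treated patient who dies or leaves before any efficacy assessment is counted. Define the visit window for the 24-month assessment, so that a slightly early scan is not a failure by default.

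Add as a sensitivity analysis the Kaplan-Meier 24-month rate, censored at the last tumour assessment, with a log-log 95% interval, stated to be valid only if loss is non-informative. Make follow-up for progression and survival to 24 months the rule after withdrawal, as Section 7.2 already allows, and reconcile this with the sealing of data in Section 4.3.

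**Cost.** The text change is short, but power must be restated. At 19 patients it is 82% with no loss and about 68% with 10% independent loss, so the stated 80% is not kept. Either accept and state that figure, or enlarge the trial. With 26 patients and a cut-off of 10, the size is 2.3% with complete data and the power 80.6% at 10% loss. The exact test is uneven in n: on the same assumptions 25 patients give 75.8% and 27 give 73.7%, so 26 leaves no margin for exclusions. Better follow-up after withdrawal reduces the loss of power directly.
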